2.3.2.2 SENSITIVITY ANALYSES

Sensitivity analyses will be performed to assess the impact of missing data on the primary endpoint results. These analyses will be conducted on the ITT population. Two techniques will be employed: the Last Observation Carried Forward (LOCF) method and the Tipping Point analysis (Yan, 2009).

The LOCF method will impute any missing Week 12 urine leakage with the most recent value collected. The difference in the proportions of responders and a 95% CI of the difference in proportion of responders will be calculated using the normal approximation to the binomial distribution. The p-value for superiority will also be reported, based on a Chi-Square test. The total number of successes in each study arm will be summarized, along with the corresponding proportions and exact 95% CIs.

The Tipping Point analysis will be performed directly on the binary endpoint of subject responder (i.e. whether or not the subject achieved ‘significant improvement’). It will be implemented as follows:

1. Determine the number of missing values in each treatment arm:
Let n_{1m} = number of missing values in the Vital Compact group
Let n_{2m} = number of missing values in the itouch Sure Pelvic Floor Exerciser group
2. Impute the missing data in each group so that all possible combinations of responder/non-responder are considered. Starting at 0 and ending at n_{1m} , the responder rate in the Vital Compact group will be changed by adding 1 responder at a time. Meanwhile, the responder rate in the itouch Sure Pelvic Floor Exerciser group will also be changed by adding 1 responder at a time, starting at 0 and ending at n_{2m} . The difference in the proportions of responders and a 95% CI of the difference will be calculated for each case.
The algorithm is as follows:
 - a. Let s_1 represent the number of responders within the group of missing Vital Compact data.
Let s_2 represent the number of responders within the group of missing itouch Sure Pelvic Floor Exerciser group data.
 - b. Set $s_1 = 0$
 - c. Set $s_2 = 0$
 - d. Calculate the difference of proportions and associated 95% confidence interval.
 - e. $s_2 = s_2 + 1$, where $s_2 \leq n_{2m}$
 - f. Repeat steps (d) to (e).
 - g. $s_1 = s_1 + 1$, where $s_1 \leq n_{1m}$. Continue to steps (c) to (f).
3. Present the lower 95% confidence limit for each possible missing data combination.

2.3.3 KEY SECONDARY ENDPOINTS

The key secondary endpoints listed below will be tested only if the primary efficacy endpoint is met. In order to control the type I error rate, the endpoints will be analyzed hierarchically. If an endpoint in the sequence fails to show statistical significance, then no statistical claims can be made for the subsequent endpoints in the hierarchy and further testing will be performed for exploratory purposes only. The analyses will be based on ITT population and the LOCF method will be used to impute missing data.

1. Between group comparison of mean change, with respect to baseline, in urine leakage in a provocative pad weight test at Week 12;
2. Within Vital Compact group estimate of mean change, with respect to baseline, in urine leakage in a provocative pad weight test at Week 12;

3. Between group comparison of mean change, with respect to baseline, in urine leakage in the 24-hour pad weight test at Week 12;
4. Within Vital Compact group estimate of mean change, with respect to baseline, in urine leakage in the 24-hour pad weigh test at Week 12;
5. Between group comparison of mean change, with respect to baseline, in the number of incontinence episodes/day recorded using a 7-day voiding diary at Week 12;
6. Within Vital Compact group estimate of mean change, with respect to baseline, in the number of incontinence episodes/day recorded using a 7-day voiding diary at Week 12;
7. Between group comparison of the mean improvement, with respect to baseline, in Incontinence Quality of Life Questionnaire (I-QOL) score at Week 12;
8. Within Vital Compact group estimate of mean improvement, with respect to baseline, in Incontinence Quality of Life Questionnaire (I-QOL) score at Week 12;
9. Between group comparison of mean change, with respect to baseline, in the number of pads used/day recorded using a 7-day voiding diary at Week 12;
10. Within Vital Compact group estimate of mean change, with respect to baseline, in the number of pads used/day recorded using a 7-day voiding diary at Week 12;
11. Between group comparison of the proportion of subjects achieving dryness at Week 12 (<1 g on the provocative pad weight test).

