8.11.1 Early Termination

If a subject starts treatment discontinues before completing all study visits, she is to be asked to return to the clinic to complete a Visit 4 visit as an early termination visit (if prior to that visit) or a Visit 5 visit (if after Visit 4 has taken place).

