10.3.4 Analysis Methods

For the primary analysis variable (proportion of patients who respond at Week 12) the difference in the proportions of responders and a 95% CI of the difference in proportion of responders will be calculated using the normal approximation to the binomial distribution. The ITT population will serve as the primary analysis population, with PP population analyses serving as supportive. For the ITT analysis, if a subject does not complete the 12 week assessment, their outcome will be imputed using multiple imputations. Non-inferiority will be claimed if the lower limit of the 95% CI is greater than -5%.

The total number of successes in each study arm will be summarized, along with the corresponding proportions and 95% CIs. The difference between proportions will also be summarized with its corresponding 95% CI.

Sensitivity analyses will be performed to assess the impact of missing data on the primary endpoint results. These analyses will be based on the ITT population. A last observation

carried forward (LOCF) method will be used to account for all missing data. A tipping point analysis will also be performed (Campbell et al., 2011 and Yan X. et al., 2009).

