10.3.7 Analysis Methods

Analysis of secondary endpoints will be based on the ITT population. All available data will be used, and no imputation is planned for missing data. The Week 12 summaries for each device group will include the number of observations, mean, median, standard deviation, minimum, maximum, and 95% confidence interval. The difference between device groups will be summarized using mean change, standard deviation, and 95% confidence interval of the difference. P-values will be obtained from two-sample t-tests for key-secondary endpoints 1, 3, 5, 7, and 9. For key-secondary endpoint 11, the proportion and counts of subjects achieving dryness at Week 12 will be summarized by group, along with 95% confidence interval. The difference between device groups will be summarized with the 95% confidence interval for the difference. The p-value from the comparison will be based on a chi-square test. One-sample t-tests will be used for key-secondary endpoints 2, 4, 6, 8, and 10. In the event that data are highly non-normal, non-parametric methods may be employed (i.e. signed-rank test, rank-sum test).

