1.6.2 GENERAL PRINCIPLES

Data will be summarized using descriptive statistics. For continuous measures, this will include number (N), mean, standard deviation, median, and range (minimum and maximum). For categorical measures, counts and percentages will be provided. Data will be summarized separately for each randomized arm under the principles of intent to treat, unless otherwise noted. All statistical tests will be conducted at $\alpha = 0.05$, two-sided significance level, unless otherwise stated. The day of randomization is considered as Day 1 and the day prior to randomization is Day -1. Summaries will be based on the database visits, regardless of the relative day of the visit; early termination visits are to be collected as Week 12 and all follow-up assessments are collected as Week 26.

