2.3.2.1 PRIMARY ENDPOINT ANALYSIS

To test these hypotheses, the difference in the proportions of responders and a 95% Confidence Interval (CI) of the difference in proportion of responders will be calculated using the normal approximation to the binomial distribution. Non-inferiority will be claimed if the lower limit of

the 95% CI is greater than -5%. Furthermore, superiority will be claimed if the lower limit of the 95% CI is greater than 0%. The p-value for superiority will also be reported, based on a Chi-Square test. The total number of successes in each study arm will be summarized, along with the corresponding proportions and exact 95% CIs.

The ITT population will serve as the primary analysis population. For this analysis, if a subject does not complete the 12 week assessment, their outcome will be imputed using multiple imputations (Schafer, 1997). The multiple imputation methodology will be implemented as follows:

1. Ten imputed datasets will be generated to impute missing urine leakage using the below SAS code. Only the imputed values at Week 12 will be retained.

```
Proc MI NIMPUTE=10 SEED=20150930 MIN=0 0 0 MAX= . . .;  
  var base w4 w12;  
  fcs reg(base) reg(w4) reg(w12);  
run;
```

2. The ten imputed datasets will be analyzed separately. Using the methodology described above, the Week 12 urine leakage will be compared against the baseline weights to classify subject responders.
3. The proportion of responders in each treatment group, along with the associated standard error, will be calculated for each of the ten imputed datasets. The individual proportion estimates and standard errors will be pooled by treatment using the SAS code below.

```
Proc MIANALYZE;  
  modeleffects prop;  
  stderr se_prop;  
  by trt;  
run;
```

4. The difference in the proportions of responders and the standard error of the difference will be calculated for each of the ten imputed datasets. The individual estimates of the difference in proportions, as well as the associated standard errors of the differences, will be pooled using the SAS code below.

```
Proc MIANALYZE;  
  modeleffects prop_diff;  
  stderr se_diff;  
run;
```

A supportive analysis will also be conducted using similar methodology in the PP population.

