4 CHANGES FROM STATISTICAL METHODS IN PROTOCOL

The protocol defined significant improvement as greater than 50% reduction in pad weight from baseline. This was clarified to be a 50% reduction in urine leakage, which is determined from the difference in pad weights pre and post testing.

The protocol planned to use both ITT and PP populations for the analyses of sensitivity, poolability, and subgroups. This was revised to only conduct these analyses on the ITT population.

The subgroup of mean intensity of the stimulation delivered during the 12-week treatment programme was only planned to be presented for urine leakage on the provocative pad weight test at Week 12. This was revised to also present this subgroup for the primary endpoint (significant improvement) at Week 12.

The subgroup of race was only planned to be presented for the primary endpoint at Week 12. This was revised to also present this subgroup for the change in urine leakage on the provocative pad weight test at Week 12.

The protocol provided ranges for the severity of urinary stress incontinence based on the 24-hour pad weight tests, but the ranges were incorrectly stated (1-hour pad weight test ranges were provided in error). This was revised to use the appropriate ranges per the O’Sullivan reference.

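### The SAP uses LOCF for all eleven key secondary endpoints where the protocol plans no imputation, and its list of changes does not declare this

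*SAP*

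**What the plan says.** **Protocol 10.3.7**, on the secondary endpoints in the ITT population: "All available data will be used, and no imputation is planned for missing data". The same paragraph assigns t-tests and a chi-square test to key secondary endpoints 1 to 11 by number, so the rule covers them.

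**SAP 2.3.3**, directly above the same eleven endpoints: "The analyses will be based on ITT population and the LOCF method will be used to impute missing data". SAP 2.3.3.1 to 2.3.3.3 give the tests and do not alter this.

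**Where the protocol uses LOCF.** Protocol 10.3.4 has it only as a sensitivity analysis of the primary endpoint, where a last-observation "carried forward (LOCF) method will be used to account for all missing data".

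**The primary endpoint in the SAP.** SAP 2.3.2.1: "if a subject does not complete the 12 week assessment, their outcome will be imputed using multiple imputations". LOCF is again a sensitivity analysis (SAP 2.3.2.2): "The LOCF method will impute any missing Week 12 urine leakage with the most recent value collected".

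**Early termination.** Under Protocol 8.11.1, a woman who stops before Visit 4 "she is to be asked to return to the clinic to complete a Visit 4 visit as an early termination visit". SAP 1.6.2 adds that "early termination visits are to be collected as Week 12 and all follow-up assessments are collected as Week 26".

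**SAP Section 4** declares five changes: pad weight clarified to urine leakage, the analysis set for three groups of analyses ("This was revised to only conduct these analyses on the ITT population"), the stimulation-intensity subgroup, the race subgroup and the severity ranges.

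**The concern.** The protocol leaves additional detail to the SAP, but this is a reversal of a stated rule, with no reason recorded. The tests run in a fixed sequence with a view to labelling. If any Week 12 value is missing, the two documents give different patient numbers, estimates and p-values, and a reader cannot tell which analysis was the prespecified one.

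There is also a statistical reason to settle it. LOCF treats a carried value as if it had been observed at Week 12. It can bias a between-group difference if leakage is still changing after the carried visit and either missingness or the time course differs by arm. For endpoints 1, 2 and 11 the SAP accepts this for a measurement that it multiply imputes for the primary endpoint.

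LOCF is described only for provocative-test leakage (SAP 2.3.2.2, 2.6 and 2.7). Read plainly, the description includes baseline. No section says whether baseline may be carried for the 24-hour pad, diary or I-QOL endpoints. A woman with no post-baseline value would then be either excluded or scored as zero change.

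**Working it through.** **1. The text.**

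| | Protocol 10.3.7 | SAP 2.3.3 |
|---|---|---|
| Endpoints | Key secondary 1–11 | Key secondary 1–11 |
| Population | ITT | ITT |
| Missing Week 12 value | Left missing | LOCF |
| Declared in SAP Section 4 | – | No |

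This step needs no assumed number.

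**2. Numbers analysed.** The plan states no dropout rate, so the missing share p is assumed. Available data use 180 × (1 − p) women. LOCF uses up to 180, but reaches 180 only if baseline may be carried for women lost before Week 4. With equal SDs, the LOCF standard error is √(1 − p) times the available-data one.

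| p | Available data | LOCF, at most | SE smaller by |
|---|---|---|---|
| 5% | 171 | 180 | 1 − √0.95 = 2.5% |
| 12.5% | 157.5 | 180 | 1 − √0.875 = 6.5% |
| 20% | 144 | 180 | 1 − √0.80 = 10.6% |

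**3. Within-group endpoints.** Let f be the share of the Week 12 change already present at the carried visit. The LOCF mean is the true mean × [1 − p(1 − f)]. At p = 12.5% the shrinkage is 0.125 × 0.50 = 6.3% for f = 0.5, 0.125 × 0.25 = 3.1% for f = 0.75 and 0.125 × 0.11 = 1.4% for f = 0.89. There is none if improvement has stopped by the carried visit. The value 0.89 is 87.43/97.71, Week 1 over Week 8 in the first-generation pilot (n = 9, Protocol 2.1). It is the only early time course in the documents.

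**4. Between-group endpoint 1, simulated with no true difference.** All inputs except the arm size and the 3–90 g range are assumed: 90 per arm; baseline 3 + 87 × Beta(1.2, 2.2), which keeps it within the eligibility range (Protocol 6.2); fractional reduction Normal(0.65, 0.35) clipped to [−1, 1]; Week 4 = baseline × (1 − f × reduction + noise, SD 0.15); dropout after Week 4. Selective dropout puts 80% of losses among women with below-median Week 4 response. Runs used 6,000 to 20,000 trials.

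| Dropout | f | LOCF error | Available-data error | Rejection, LOCF v available |
|---|---|---|---|---|
| Selective, 10% v 20% | 0.75 | about 0.5 g | about 0.6 g, opposite sign | both near 5% |
| Selective, 10% v 20% | 0.89 | about 0.3 g | about 0.6 g, opposite sign | 5.4% v 5.1% |
| 15% in both arms | 0.9 v 0.5 by arm | about 1.1 g | about 0.2 g | 7.1% v about 5% |
| Random, 10% v 20% | 0.5 | about 1.0 g | about 0 | 7.0% v about 5% |
| Random, 10% v 20% | 0.75 | about 0.5 g | about 0 | 5.4% v about 5% |
| Random, 10% v 20% | 0.89 | about 0.2 g | about 0 | 5.1% v about 5% |

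In the 10% v 20% cases LOCF favours the arm with less dropout. Under selective dropout, available data favour the arm with more, because poor responders leave it.

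Hand check of the random rows: the mean baseline is 3 + 87 × 1.2/3.4 = 33.7 g. The mean reduction after clipping is 0.65 − 0.35 × (0.242 − 0.159) = 0.62. The mean change is therefore 33.7 × 0.62 = 20.9 g. The LOCF error is 20.9 × (1 − f) × 0.10 = 1.0, 0.5 and 0.2 g.

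**5. The extreme.** If every missing woman had only baseline to carry (f = 0), the same formula gives 20.9 × 0.10 = 2.1 g. A standardised simulation with a true change of 1 SD in both arms and 10% v 20% random missingness rejects 11.4% of the time with LOCF and 5.1% with available data. This bounds the effect at that dropout split. It is not an estimate.

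**6. The gate.** With equal responder rates r and 90 per arm, non-inferiority is met with probability P(Z > 1.96 − 0.05/√(2r(1 − r)/90)), which is 9.9% at r = 0.52 and 11.1% at r = 0.71. A false endpoint 1 claim needs both this and rejection, so its probability cannot exceed the smaller of the two.

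**The case against.** **LOCF need not be the worse rule.** This stands. With selective dropout at f = 0.75 the two rules err by similar amounts. At f = 0.89, the only value with a source in the documents, LOCF errs by about half as much as available data. The 7.1% case needs a time course that differs by arm, and nothing in the documents supports or excludes that.

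**Little is left to impute.** This stands in part. The provocative test and I-QOL are done at the visit (Protocol 8.11.5), so a returning early terminator has values for endpoints 1, 2, 7, 8 and 11. The 24-hour pads and the diary are filled in at home over the preceding days, so an unplanned visit may or may not bring them.

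**The remedy is a preference.** In part. Reconciling and declaring would cure the documentary fault. But neither existing rule is dependable, and the SAP already uses multiple imputation for the primary endpoint. In the simulation, arm-specific regression on baseline and Week 4 errs by under 0.1 g. That is built in, because dropout there depends only on Week 4. It shows what the method achieves under missing at random and nothing about other mechanisms.

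**The versions may differ.** The SAP cites protocol version 2.0, and the title page of the supplied protocol was removed. SAP Section 4 also says the protocol planned sensitivity analyses in both populations, whereas Protocol 10.3.4 names ITT only. A version difference is possible, but the conflict between the supplied documents remains.

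**Conclusion.** The point holds as an undeclared conflict between protocol and SAP over missing data for all eleven key secondary endpoints, together with uneven handling of the same pad weight within the SAP. That conclusion rests on the text alone.

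The practical size is unknown and may be small. It depends on how many Week 12 values remain missing after early-termination visits are counted, on how much of the change is present at the carried visit, and on differences between arms. All the grams and rejection rates above are illustrations from assumed inputs.

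Three stronger readings do not follow:

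- **That LOCF will produce false label claims.** Endpoint 1 is tested only after the primary endpoint is met, and endpoints 2 to 11 support a claim only after endpoint 1 succeeds. Rejection is near 5% in most of the cases examined.
- **That the protocol's rule is the sound one.** With selective dropout it is biased too.
- **That the rule was changed to gain significance.** No reason is given in either direction, and LOCF can lower or raise an estimate.

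**What to change.** 1. Reconcile Protocol 10.3.7 with SAP 2.3.3 before unblinding, and enter the choice and its reason in SAP Section 4.
2. As the main analysis, use multiple imputation with treatment arm, baseline and Week 4 for each endpoint, and derive endpoint 11 from the imputed pad weight. The code in SAP 2.3.2.1 already has baseline and Week 4 but not arm. Alternatively, use a repeated-measures model for the continuous endpoints, with multiple imputation for endpoint 11. State that both assume data missing at random.
3. Keep the available-data and LOCF analyses as sensitivity analyses. Define LOCF for each endpoint and say whether baseline may be carried.

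The cost is SAP wording and modest programming. Pooling rules are needed for the chi-square test (SAP 2.3.3.2) and for any rank-based fallback (SAP 2.3.3.1 and 2.3.3.3). For endpoint 11, the pooled difference in proportions and its standard error, as SAP 2.3.2.1 already sets out for the primary endpoint, could serve. No new data are required.

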2.3.3.1 ANALYSIS OF BETWEEN-GROUP MEAN CHANGES FOR KEY SECONDARY ENDPOINTS

For the between-group comparisons of mean change (endpoints 1, 3, 5, 7, and 9 in the hierarchy noted above), the key secondary hypothesis is that the mean change from baseline to Week 12 for Vital Compact is not equal to that of itouch Sure Pelvic Floor Exerciser:

$$H_0: \mu_{Vital\ Compact} = \mu_{control}$$

$$H_1: \mu_{Vital\ Compact} \neq \mu_{control}$$

where $\mu_{Neurotech\ Vital\ Compact}$ is the mean change from baseline for the Vital Compact group and $\mu_{control}$ is the mean change from baseline for the itouch Sure Pelvic Floor Exerciser group.

To test this hypothesis, a two-sample t-test will be conducted for each endpoint. The difference between device groups will be summarized using mean change, standard deviation, and a 95% confidence interval of the difference. In the event that data are highly non-normal, non-parametric methods (e.g. rank-sum test) may be employed. Normality will be tested using Shapiro Wilk Test.

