11.5 Maintenance of Randomisation and Blinding

A randomisation schedule will be provided. The randomisation schedule is in a permuted block-format randomisation, stratified by study site, to ensure that the subject allocation at the sites remains balanced.

The Subject ID number, randomisation date and patient initials will be recorded along with the allocated treatment.

It is not anticipated that there will be any need to unblind (break the randomisation code) of any subject participating in the study because of an adverse event/adverse device effect, however, the information will be available at the site via the unblinded personnel.

One member of the investigational site team will be responsible for patient training and will consequently be unblinded to required treatment instructions for training. A different member of the team will be responsible for all other patient assessments and CRF completion.

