1.4 SAMPLE SIZE AND POWER

Sample size calculations were performed using the NQuery Advisor® version 5.0, under a two group test of proportions.

Research suggests that the response rates for Vital Compact and itouch Sure at 12 weeks will be 71% and 46%, respectively (itouch success rate based on Sand, 1995).

The sample size calculation is based on the assumption that the itouch Sure Pelvic Floor Exerciser success rate is 52% and the Vital Control success rate is 71%. A sample size of 87 subjects per group will provide 90% power using a one-sided Type I error rate of 0.025, and a non-inferiority margin of 5%. A randomization allocation of 1:1 was also assumed. For practical reasons, the sample size has been increased to a recruitment of 180 subjects (90 subjects per treatment group).

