2.6 POOLABILITY ANALYSIS

A poolability analysis will be performed on the primary endpoint to test for a differential treatment effect across study centres. The primary endpoint will be summarized by study centre. Poolability will be assessed using a logistic regression model. The logistic regression model will include a covariate for the treatment arm, study centre, and interaction effect of treatment by centre. The p-value for the interaction effect will be provided. These analyses will be performed for the ITT population. The LOCF method will be used, imputing missing Week 12 urine leakage with the most recent value collected. A single centre will be used to pool small sites (<4 subjects) for the logistic regression.

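### Key secondaries 1, 3, 5, 7 and 9: ANCOVA with baseline and site tests the same mean-change hypothesis as the planned unadjusted t-test, and would pass the gatekeeping endpoint 1 more often than that t-test if a true difference exists

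*SAP*

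**What the plan says.** In SAP 2.3.3.1 the hypothesis for endpoints 1, 3, 5, 7 and 9 is that "the mean change from baseline to Week 12 for Vital Compact is not equal to that of itouch Sure Pelvic Floor Exerciser". The test follows: "To test this hypothesis, a two-sample t-test will be conducted for each endpoint". Protocol 10.3.7 agrees: "P-values will be obtained from two-sample t-tests for key-secondary endpoints 1, 3, 5, 7, and 9".

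There is an optional fallback: "In the event that data are highly non-normal, non-parametric methods (e.g. rank-sum test) may be employed". SAP 2.3.3.1 names Shapiro-Wilk as the check of normality, and SAP 1.6.2 sets a default two-sided 0.05 level for all tests.

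Neither document puts baseline or site into a model for these endpoints. Both are available. The schedule of events (Protocol Appendix I) shows each measure at baseline, and Protocol 11.5 describes a "permuted block-format randomisation, stratified by study site". Site is used as a covariate only in the logistic poolability model for the primary endpoint, where SAP 2.6 also gives a rule for sparse sites: "A single centre will be used to pool small sites (<4 subjects) for the logistic regression".

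The key secondaries form a fixed sequence (SAP 2.3.3): "If an endpoint in the sequence fails to show statistical significance, then no statistical claims can be made for the subsequent endpoints". The same section plans LOCF for missing data. No effect size, SD, baseline correlation or power is stated for any key secondary.

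**The concern.** A t-test on change amounts to fixing the coefficient of baseline at 1. Where the true slope of the Week 12 value on baseline differs from 1, baseline variation that the trial has already measured stays in the error term. ANCOVA estimates the slope instead.

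This matters most at endpoint 1, the between-group comparison of change on the provocative pad test. It stands first, so a miss there ends formal claims on the ten endpoints behind it, and Protocol 5.2 says these endpoints are meant to support labelling. The primary non-inferiority test and the nested superiority test are not touched.

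**Working it through.** **The plan's own figure.** The only sample size stated is for the primary endpoint. With 71% v 52%, mean rate 0.615, margin 5%, one-sided 0.025 and 90% power:

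n = 2 × 0.615 × 0.385 × (1.960 + 1.282)² / (0.19 + 0.05)² = 86.4, so 87 per group.

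This reproduces the stated 87. Nothing comparable exists for endpoint 1, so its power has to be explored under assumptions.

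**The exact part.** Let SDb and SDw be the baseline and Week 12 SDs and r their correlation, taken as common to both arms.

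- Var(change) = SDb² + SDw² − 2·r·SDb·SDw
- Var(ANCOVA residual) = SDw²·(1 − r²)
- Difference = (SDb − r·SDw)², which cannot be negative. It is zero only when the slope r·SDw/SDb equals 1.

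Under randomisation the ANCOVA treatment coefficient on untransformed change estimates the same difference in mean change, so H0 and H1 stand. The cost is 12 of 178 degrees of freedom (1 for baseline, 11 for about 12 sites), at most about 0.1 percentage point of power.

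**Endpoint 1 grid.** Assumed: 5 g true difference, 90 per arm, r = 0.5, and the baseline SDs shown. The Week 12 SD is either 13.19 g (pilot, Protocol 2.1) or 20 g (assumed). Power = Φ(5 / (SD·√(2/90)) − 1.96). The pilot baseline SD of 43.92 g is not used, because the 3-90 g entry range caps the SD at (90 − 3)/2 = 43.5 g.

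| Week 12 SD | Baseline SD | SD of change / ANCOVA (g) | Power, t-test to ANCOVA |
|---|---|---|---|
| 13.19 g | 9 g | 11.67 / 11.42 | 82% to 84% |
| 13.19 g | 12 g | 12.64 / 11.42 | 76% to 84% |
| 13.19 g | 15 g | 14.18 / 11.42 | 66% to 84% |
| 13.19 g | 21 g | 18.38 / 11.42 | 45% to 84% |
| 20 g | 9 g | 17.35 / 17.32 | 49% to 49% |
| 20 g | 12 g | 17.44 / 17.32 | 49% to 49% |
| 20 g | 15 g | 18.03 / 17.32 | 46% to 49% |
| 20 g | 21 g | 20.52 / 17.32 | 37% to 49% |

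**Other endpoints, Var(change) / Var(ANCOVA).**

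- Endpoint 3, pilot 24-hour baseline SD 19.41 g, r = 0.5: 17.41²/4.47² = 15 with the pilot Week 12 SD of 5.16 g, 2.7 with an assumed 12 g, and 1.33 if the SD does not shrink.
- Endpoint 5, pilot SDs 2.81 and 2.28 leaks/day (the second is a Week 26 value): 1.72 at r = 0.5 and 1.56 at r = 0.7.
- Endpoints 7 and 9, no SDs given: with equal SDs the ratio is 2/(1 + r), so 1.33 at r = 0.5 and 1.18 at r = 0.7.

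With equal SDs, a t-test with 80% power corresponds to ANCOVA power of 93.5%, 89.9%, 85.9% and 81.9% at r = 0.3, 0.5, 0.7 and 0.9.

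**Simulations calibrated to 71% v 52% responders.** 90 per arm, 12 sites, baseline log-normal truncated to 3-90 g. Distribution shapes are assumptions.

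- 15 scenarios, 4,000 trials each, no site effect, complete data. Two-class response: t-test 35-40%, ANCOVA 46-51%. Log-normal Week 12/baseline ratio: t-test 45-69%, ANCOVA 63-75%. The gain was 0 to 26 points, and ANCOVA was never below the t-test.
- 12 scenarios, 2,000 trials each, log-ratio SD 0.6 to 1.2, site SD 0 or 0.3. T-test 38-61%, ANCOVA with baseline 55-71%, with baseline and site 56-71%. The gain was about 3 to 28 points, of which site contributed about 0 to 4.
- With 15% of subjects (assumed) having baseline carried forward, the gain was about 1 to 15 points, against about 1 to 26 in matching complete-data runs.

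**Type I error with identical arms.** ANCOVA 4.4-5.0% and t-test 5.0-5.1% in the first set; ANCOVA 4.0-5.3% in the second.

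**The case against.** The strongest objection concerns the comparator. Pad weights are bounded and skewed, and Shapiro-Wilk rejected in 96-100% of simulated trials, so the rank-sum fallback may well be the test used. Against it, ANCOVA ranged from 8 points below to 22 above. In one high-noise scenario rank-sum had 69.8% power against 63.7%, and in the two-class scenarios the two were about level. A reader might infer that ANCOVA makes endpoint 1 more likely to pass whichever planned test is used. That does not hold. What remains is that the rank-sum test does not test the stated difference in means.

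Three further points stand.

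- The largest gains in the grid pair a Week 12 SD from 14 pilot subjects, treated with an earlier-generation device, with assumed baseline SDs, and apply it to both arms. At 20 g the gain is 0 to 12 points.
- A reader might infer that the normality switch has no threshold. Shapiro-Wilk read at the 0.05 level of SAP 1.6.2 arguably supplies one. What stays open is how far from normal counts, and that the switch is permitted rather than required.
- Removing the rank-based fallback is a trade-off. With equal mean change but strongly unequal spread (log SD 0.8 v 1.2), type I error was 6.5-7.2% for ANCOVA, 5.8-6.3% for the t-test and 15-19% for rank-sum.

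None of this argues for leaving baseline out of the test of means.

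**Conclusion.** The point holds as an improvement at almost no cost, not as an error: the planned t-tests are valid. Compared with the t-test, ANCOVA keeps the hypothesis, holds type I error near 5% with identical arms, and makes endpoint 1 more likely to pass if the devices truly differ. The variance inequality is exact under a common covariance structure. The size of the gain is not fixed by the documents: about 0 to 28 points with complete data, less under the planned LOCF, and near zero when the slope on baseline is close to 1. Nearly all of it comes from baseline. Site is included chiefly because the randomisation is stratified by it. Confidence in the direction is high; confidence in any particular gain is low, since the SDs, correlations and dropout rate are assumptions or small-pilot values.

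**What to change.** In SAP 2.3.3.1, replace the two-sample t-test for endpoints 1, 3, 5, 7 and 9 by ANCOVA on the untransformed change from baseline, with treatment, baseline value and site, pooling sites with fewer than 4 subjects as in SAP 2.6. Report the adjusted difference with its 95% CI and p-value. Keep the unadjusted t-test as a sensitivity analysis. List the departure from Protocol 10.3.7 in SAP section 4. The hierarchy and endpoints 2, 4, 6, 8, 10 and 11 stay as planned.

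Recommended separately, as a sponsor choice rather than a free change: make the ANCOVA the single confirmatory test and move the rank-based test to sensitivity, so that the choice of test is not left open once the data are seen.

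The cost is SAP wording and one section 4 entry before unblinding, plus up to 12 degrees of freedom. No patients, visits or data are added.
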